3.4 Analysis Timepoints for e-diary Questionaries

The analysis timepoints will be derived for questionaries collected via e-diary (for an extract based on Data Export Specification 2.0) as defined in Table 3.

The study day will be calculated as the following:

$$Study Day = (Completed Date) - (Randomization Date) + 1.$$

Adverse events, medication usage and patch application data collected via e-diary will not be used for analysis. Those are being transcribed by the site from the diary into the CRF database that will be used for analysis.

In consistency with Section 3.1, assessments collected at Day 1 Visit 1 will be considered as the baseline (if for FIRTECH Patch arm the assessment was done before the Patch application). Analysis timepoints "Baseline" and "Day 5 Visit 2" are derived only for on-site evaluations.

CONFIDENTIAL Page 14 of 30

Table 3: Analysis Timepoints for eDiary

Study Day	Questionnaire Name	Analysis Timepoints
Day 1ª	Daily Diary (Visit 1 Day 1) or Evening Daily Diary when Protocol Deviation (PD) comment completed as mentioned in the NTF number: 019, dated 22 Nov 2022 and when the associated PD occurrence date is equal to the CRF Visit 1 date.	Baseline
Day 1	Roland-Morris Disability Questionnaire	Baseline
Day 1	Evening Daily Diary	Day 1 Evening
Day 2	Morning Daily Diary	Day 2 Morning
Day 2	Evening Daily Diary	Day 2 Evening
Day 3	Morning Daily Diary	Day 3 Morning
Day 3	Evening Daily Diary	Day 3 Evening
Day 4	Morning Daily Diary	Day 4 Morning
Day 4	Evening Daily Diary	Day 4 Evening
Day 5	Morning Daily Diary	Day 5 Morning
Day 5 ^a	Daily Diary (Visit 2 Day 5) or	Day 5 Visit 2
	Morning Daily Diary when PD comment completed as	
	mentioned in the NTF number: 019, dated 22 Nov	
	2022 and when the associated PD occurrence date is	
	equal to the CRF Visit 2 date.	
Day 5	Roland-Morris Disability Questionnaire	Day 5 Visit 2

^a According to the Memo to file "CRF Documentation of on-site Day 1 Visit 1 and Day 5 Visit 2 assessments done in the evening and in the morning respectively" (NTF number: 019, dated 22 Nov 2022) there are instances of subjects having their on-site eDiary evaluations ("Daily Diary (Visit 1 Day 1)" and/or "Daily Diary (Visit 2 Day 5)") incorrectly recorded as at-home evaluations ("Evening Daily Diary" and/or "Morning Daily Diary" respectively). Per this memo, this data issue cannot be updated at the data level. In addition to that, there were entered special documented PDs that can be considered as confirmation from the site that corresponding measurements were indeed collected on-site during the corresponding Visit 1/ Visit 2. Therefore, subjects with these specific PDs will be analyzed as one having their on-site evaluations collected with their specified eDiary records ("Evening Daily Diary" and/or "Morning Daily Diary" respectively) considered as corresponding on-site evaluations ("Daily Diary (Visit 1 Day 1)" and/or "Daily Diary (Visit 2 Day 5)"), including the derivation of baseline, populations, and Analysis Timepoints.

CONFIDENTIAL Page 15 of 30

4 ANALYSIS POPULATION AND TREATMENT GROUPS

4.1 Analysis Populations

The following populations will be considered for the study:

4.1.1 Intent-to-Treat (ITT) Population

The ITT population will be defined as all subjects randomized. This population will be used for demographic analysis.

4.1.2 Modified Intent-to-Treat (mITT) Population

The mITT population will be defined as all subjects randomized that had the NRS evaluation done at baseline and Day 5 Visit 2 with the exclusion of subjects without any pain at baseline (i.e. baseline instantaneous pain NRS score equal to "0"). This population will be used for the primary endpoint analysis.

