4.1.3 Full Analysis Set (FAS)

The FAS population will be defined as all subjects randomized that had the NRS evaluation done at baseline and that were not using any rescue medication (as defined in Section 5.1.7.4.2) starting from randomization to Day 5 Visit 2 or starting before the study and still ongoing at randomization with the exclusion of subjects without any pain at baseline (i.e. baseline instantaneous pain NRS score equal to "0"). This population will be used for key secondary, other secondary and exploratory analyses.

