4.1.4 Sensitivity Analysis Population

The Sensitivity Analysis population will be defined as all subjects from the mITT population with the exclusion of subjects with protocol deviations described in the Memo to file "CRF Documentation of on-site Day 1 Visit 1 and Day 5 Visit 2 assessments done in the evening and in the morning respectively" (NTF number: 019, dated 22 Nov 2022). The algorithm for excluding subjects from this population may be expanded based on a review of analysis results and such extensions will be documented separately.

This population will be used for the sensitivity analysis of primary endpoint.

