5 ANALYSIS METHODS

5.1.1 Disposition

Disposition will be summarized descriptively using counts and percentages for All Subjects by treatment group and overall. The number and percentage of subjects screened, screen failures, randomized and completed the study will be presented, together with number and percentage of subjects who prematurely discontinued from the study along with reasons for study discontinuation will be summarized.

A listing of subject's disposition status will be provided. The number of subjects in each analysis population will be summarized descriptively with counts and percentages separately. A listing of subject's inclusion to analysis sets will be provided. A subject's eligibility with inclusion/exclusion criteria completions or violations will be listed.

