5.1.7 Efficacy Analysis

5.1.7.1 Primary Analysis

Instantaneous pain on NRS will be summarized for actual values and change from baseline with descriptive statistics for the ITT and FAS populations by treatment group and by analysis timepoint (from Baseline to Day 5 Visit 2).

NRS-response will be defined as $\geq 30\%$ decrease from the baseline of the instantaneous pain and no rescue medication (Section 5.1.7.4.2).

CONFIDENTIAL Page 19 of 30

The number and percentage of NRS-responders at Day 5 Visit 2 will be presented descriptively by treatment groups, along with associated 95% confidence intervals.

The difference in the rate of responders at Day 5 Visit 2 will be tested between treatment groups using two-sided Fisher's exact test at the 5% error level (alpha = 0.05) and presented with its associated p-value. The null hypothesis H_0 that there is no difference in the rate of responders will be tested against the alternative hypothesis H_A that there is a difference in the rate of responders:

$$H_0: p_T - p_C = 0$$

$$H_A: p_T - p_C \neq 0$$

Where p_T denote the rate of responders at Day 5 Visit 2 in the FIRTECH Patch treatment group (treatment, T) and p_C denote the rate of responders at Day 5 Visit 2 in the No Patch treatment group (control, C). This analysis will be based on the mITT population.

A sensitivity analysis will be conducted by executing the primary endpoint analysis for subjects from the Sensitivity Analysis population. A list of subjects excluded from the Sensitivity Analysis population will be provided along with the reason for their exclusion.

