5.1.7.4.2 Use of Rescue Medication

Rescue medication will be defined as receiving paracetamol (authorized), any other analysis and anti-inflammatory drugs as well as any non-pharmaceutical therapy (prohibited) for treating pain starting from randomization to DAY 5 Visit 2 or starting before the study and still ongoing at randomization. Each use of rescue medication will be classified according to Study Day ([Start date] – [Randomization date] + 1).

The number and percentage of subjects using rescue medication will be presented for treatment groups by Study Day (Starting from Randomization to Day 5 Visit 2, Starting before the Study and still ongoing at Randomization, Day 1, Day 2, Day 3, Day 4, Day 5) and overall.

Summary of Use of Rescue Medication will be based on the Safety population.

Additionally, all medications and non-drug treatments/procedures received on Day 6 will be listed and summarized for the Safety population.

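### The primary responder test leaves out every subject without a Day 5 Visit 2 NRS, including recorded rescue users who are non-responders by definition, and no planned responder analysis checks whether the conclusion survives that loss

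*SAP*

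**What the plan says.** - **Endpoint.** SAP 5.1.7.1 defines response as at least a 30% "decrease from the baseline of the instantaneous pain and no rescue medication". SAP 5.1.7.4.2 defines rescue broadly: authorised paracetamol, other analgesic or anti-inflammatory drugs, and non-drug therapy for pain, from randomisation to Day 5 Visit 2 or already ongoing at randomisation.
- **Primary set.** SAP 4.1.2 takes "all subjects randomized that had the NRS evaluation done at baseline and Day 5 Visit 2" and removes those with a baseline instantaneous NRS of 0. For the Fisher test, SAP 5.1.7.1 says "This analysis will be based on the mITT population".
- **Sensitivity set.** SAP 4.1.4: "The Sensitivity Analysis population will be defined as all subjects from the mITT population", less subjects with the NTF 019 recording deviations. Its rule may be extended later, but only to exclude more subjects.
- **FAS.** SAP 4.1.3 does not require a Day 5 score but removes all rescue users. It states: "This population will be used for key secondary, other secondary and exploratory analyses".
- **Reporting of loss.** SAP 5.1.1: "The number of subjects in each analysis population will be summarized descriptively with counts and percentages separately". Disposition is shown by arm. Pain scores are summarised in ITT (SAP 5.1.7.1), and rescue use is tabulated by arm (Table 14.1.3.3).
- **Withdrawals.** Protocol 7.11.1 has withdrawn subjects assessed by the Day 5 procedures where possible. SAP 3.4 says that the Baseline and Day 5 Visit 2 timepoints "are derived only for on-site evaluations", and SAP Table 3 lists the latter against Study Day 5.
- **Protocol.** Section 8.2 defines an Evaluable for Efficacy set requiring NRS at baseline and Day 5. Section 6.4.1 sizes the trial on evaluable subjects with 10% dropout.

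**The concern.** The endpoint is a composite, so the outcome of some subjects is known without a Day 5 score. A subject who took rescue on Day 2 and missed Visit 2 is a non-responder by the SAP's own definition, but the primary test ignores that subject. For the other subjects without a Day 5 score, the SAP gives no imputation, non-response or tipping-point rule. The Appendix lists only two responder tables, 14.2.2.1 on mITT and 14.2.2.2.6 on its subset.

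The plan allows for about 20 of 200 subjects being lost. The trial is open label against no patch, so loss could depend on both arm and outcome. If it does, the completer responder rate rises in the arm that loses more failures. The planned tables would show an imbalance, but not whether the Fisher result depends on it.

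**Working it through.** **1. The plan's own figure.** Pooled two-proportion formula, two-sided 5%, 80% power: n = [1.96·√(2p̄q̄) + 0.842·√(p₁q₁ + p₂q₂)]² / (p₂ − p₁)². For 20% vs 39%: [1.96·√0.41595 + 0.842·√0.3979]² / 0.0361 = 89.3, so 90. The six rows of Table 2 give 81, 90, 85, 88, 84 and 82 per arm. The maximum matches the stated 90, and 180/0.9 = 200.

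**2. Assumptions for the rest.** The documents give neither dropout nor rescue use by arm. I take 100 randomised per arm and missing counts of 10/10, 12/8 and 15/5, each averaging the planned 10%. All p-values and rejection rates come from exact enumeration of two-sided Fisher tests, rejecting at p ≤ 0.05.

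**3. Shift from dropping known failures.** Leaving out m failures of 100 at true rate r raises that arm's rate by r·m/(100 − m). For r from 30% to 60%:

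| m | Rise (points) |
|---|---|
| 2 | 0.6-1.2 |
| 5 | 1.6-3.2 |
| 10 | 3.3-6.7 |

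The last row is an extreme: it makes the whole planned dropout in that arm rescue users.

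**4. False rejection with equal all-randomised rates of 30-60%.** The completer rate is r/(1 − f·d), where d is the arm's missing fraction and f the share of missing subjects who failed. The rest are assumed to respond at the completer rate. Example: r = 60%, f = 1, 15/5 gives 0.60/0.85 = 70.6% vs 0.60/0.95 = 63.2%.

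| Missing | All failures (f = 1) | Half failures (f = 0.5) |
|---|---|---|
| 10/10 | 3.4-3.5% | 3.2-3.6% |
| 12/8 | 4.5-5.7% | 4.0-4.6% |
| 15/5 | 7.0-16.2% | 4.6-6.6% |

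**5. Dependence of a result at the 30% vs 51% row.** Counts are expected values rounded to whole subjects (exact halves to the even number). Missing = failure keeps the same responders over 100 per arm.

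| Missing patch/control | Completers, patch vs control | p | p, missing = failure |
|---|---|---|---|
| 10/10 | 46/90 vs 27/90 | 0.006 | 0.008 |
| 12/8 | 45/88 vs 28/92 | 0.006 | 0.018 |
| 15/5 | 43/85 vs 28/95 | 0.006 | 0.038 |
| 5/15 | 48/95 vs 26/85 | 0.010 | 0.002 |

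If every missing patch subject failed, significance is lost once 5 of 10 missing controls responded at 10/10 (p = 0.059), 3 of 8 at 12/8 (p = 0.058) or 1 of 5 at 15/5 (p = 0.055). That is the least favourable direction for the patch.

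**6. Borderline results.** For the smallest significant completer result with about 30% control response, missing = failure moves p from 0.045 to 0.052 (10/10), 0.046 to 0.100 (12/8) and 0.044 to 0.176 (15/5, more patch subjects missing).

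**7. Missing = failure is not neutral either.** If 15/5 dropout is unrelated to response (true rates 30-70%), the analysed rates become 0.85r and 0.95r. That rule then rejects 5.5-13.9% of the time, against 3.7-4.2% for completers.

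**8. Power of missing = failure.** If the Table 2 rates are completer rates and 10% are missing per arm, rates over 100 per arm are multiplied by 0.9. Fisher power is then 70.5-79.9% across the six rows, against 75.2-80.5% for mITT at 90 per arm.

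**The case against.** The strongest reply is that the problem is small near the planned conditions. With balanced loss the completer test stays below 5% even if every missing subject failed, and at 12/8 it reaches at most 5.7%. At the 30% vs 51% row, missing = failure stays significant in every split shown. Nobody can size the group with recorded rescue and no Day 5 score from the documents. A reader could also rebuild most of this from the planned listings of rescue use and ITT pain scores. All of that stands, and it keeps the point modest. It does not replace an analysis fixed in advance, because the choice of rule would otherwise be made after the results are known.

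Three stronger readings are tempting, and the documents do not support them:

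- **That mITT breaches the protocol.** The synopsis places efficacy under the intent-to-treat paradigm, but Protocol 8.3.1.1 names no population for the primary test, and 8.3.1.2 glosses the paradigm as analysis by randomised arm. The mITT set is close to Evaluable for Efficacy and to the sample-size basis.
- **That the test is biased towards the patch.** No figure shows which arm will lose more subjects or why. If controls lose more failures, the completer test works against the patch, as the 5/15 row illustrates.
- **That unequal loss would be hidden.** Disposition, population counts and rescue tables would show it.

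Protocol 7.11.1 may also reduce missing scores. How far is unclear, because SAP Table 3 does not say whether an on-site exit evaluation before Day 5 counts as Day 5 Visit 2. The sentence quoted from SAP 3.4 restricts place, not day. This ambiguity needs one sentence and is not evidence of bias.

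**Conclusion.** The point holds as a modest gap in robustness that should be closed. The primary test drops some subjects whose outcome is already determined, and neither planned responder analysis includes anyone with a missing Day 5 score. False-positive inflation is material only with strong imbalance and mostly failures among the missing: 7.0-16.2% at 15/5, against about 3.5% at 10/10. The effect can run in either direction. All of these sizes rest on assumed splits of the planned 10% dropout and on assumed outcomes for missing subjects. The structural gap itself follows from the SAP text alone.

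**What to change.** Keep mITT as the primary analysis. Add to SAP 5.1.7.1 two sensitivity analyses in all randomised subjects with baseline instantaneous NRS above 0, by assigned arm:

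- **(a)** All subjects with rescue use, and all subjects with a missing Day 5 Visit 2 NRS, count as non-responders.
- **(b)** A two-way tipping-point table gives the Fisher p-value for each number of responders in each arm among subjects with a missing Day 5 Visit 2 NRS and no recorded rescue use. Those with recorded rescue stay non-responders.

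The rescue definition in 5.1.7.4.2 ends at Day 5 Visit 2, which does not exist for many of the subjects being added. For subjects without Visit 2, end the window at the close of Study Day 5 or at the last available record, whichever is earlier. Treat rescue status after the last record as unknown, so that these subjects stay in the tipping-point group. This matters because rescue data are transcribed by the site from the diary (SAP 3.4), and the scheduled diary review is at Visit 2.

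Do not simply add rescue users with missing scores to mITT while still excluding the other missing subjects. That would select missing subjects by outcome.

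Read (a) together with (b). Given its lower power and its own sensitivity to unequal dropout, a non-significant (a) alone should not overturn a significant primary result.

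Separately, state under SAP Table 3 whether an on-site exit evaluation before Day 5 is mapped to Day 5 Visit 2.

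The cost is two tables, one derivation rule and one sentence. Responder rates in (a) will be slightly lower. No new data are needed, and the sample size and primary test do not change.

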4.1.3 Full Analysis Set (FAS)

The FAS population will be defined as all subjects randomized that had the NRS evaluation done at baseline and that were not using any rescue medication (as defined in Section 5.1.7.4.2) starting from randomization to Day 5 Visit 2 or starting before the study and still ongoing at randomization with the exclusion of subjects without any pain at baseline (i.e. baseline instantaneous pain NRS score equal to "0"). This population will be used for key secondary, other secondary and exploratory analyses.

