The inferential analysis of time-to-event endpoints (time to reach acceptable pain, time to reach no pain) will include summary, display, and analysis using Kaplan-Meier estimation method. The comparison of survival distributions between the group with patch and no-patch group will be done by the Log-Rank test. During the analysis, if the event if interest never occurs, the time will be censored at the final visit.

These analyses will be based on the ITT population, using the ITT paradigm (i.e. as randomized).

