5.1.7.2 Key Secondary Analyses

Key Secondary analyses will be based on the FAS population.

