5.1.7.3 Other Secondary Analyses

Other Secondary Analyses will be based on the FAS population.

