5.1.7.4 Exploratory Analyses

5.1.7.4.1 Pain Perception – Average Pain, Worst Pain and Least Pain

Pain Perception, including NRS of Average Pain, Worst Pain and Least Pain, will be summarized for actual values and change from baseline with descriptive statistics for FAS population by treatment group and by analysis timepoint (from Baseline to Day 5 Visit 2).

Change from baseline for NRS of Average Pain, Worst Pain and Least Pain at Day 5 Visit 2 will be analyzed by ANCOVA model with the treatment group as fixed effect and baseline instantaneous pain NRS as a continuous covariate.

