14.3.1.2.2	Summary of Unanticipated Adverse Device Effects by System Organ Class and Preferred Term for FIRTECH Patch Treatment Group (Safety Population)
14.3.1.2.3	Summary of Treatment-Emergent Adverse Events by System Organ Class, Preferred Term and by Severity (Safety Population)

CONFIDENTIAL Page 27 of 30

Table Number	Table Title
14.3.1.2.4	Summary of Treatment-Emergent Adverse Events by System Organ Class, Preferred Term and by
	Relationship (Safety Population)
14.3.1.2.5	Summary of Serious Treatment-Emergent Adverse Events by System Organ Class and Preferred Term
	(Safety Population)
14.3.5.1	Summary of Vital Signs (Safety Population)
14.3.5.2	Summary of Local Physical Examination (Safety Population)
14.3.6.1	Summary of Prior Medications (Safety Population)
14.3.6.2	Summary of Concomitant Medications (Safety Population)

CONFIDENTIAL Page 28 of 30

Figure Number	Figure Title
14.2.2.3.2	Other Secondary Analysis of Time Course of Pain Intensity Difference, Box Plots of Pain Intensity
	Difference (Full Analysis Set)
14.2.2.3.3	Other Secondary Analysis of Time Course of Pain Relief, Box Plots of Pain Relief (Full Analysis Set)
14.2.2.2.4	Cumulative Incidence Curve for Time (hours) to Reach Acceptable Pain (Intent-to-Treat Population)
14.2.2.3.1	Cumulative Incidence Curve for Time (hours) to Reach No Pain (Intent-to-Treat Population)

CONFIDENTIAL Page 29 of 30

Listing Number	Listing Title
16.1.7	Listing of Randomization (All Randomized Subjects)
16.2.1.1	Listing of Subject Disposition (All Subjects)
16.2.1.2	Listing of Screen Failure and Inclusion / Exclusion Criteria Assessment (All Subjects)
16.2.2	Listing of Protocol Deviations (All Subjects)
16.2.3.1	Listing of Analysis Populations (All Randomized Subjects)
16.2.3.2	Listing of Subjects Excluded from the Sensitivity Analysis Population (Modified Intent-to-Treat Population)
16.2.4.1	Listing of Subject Demographic and Baseline Characteristics (Intent-to-Treat Population)
16.2.4.2	Listing of Medical History (Intent-to-Treat Population)
16.2.4.3	Listing of Baseline Acute Low Back Pain History (Intent-to-Treat Population)
16.2.4.4.1	Listing of Prior Medications (Safety Population)
16.2.4.4.2	Listing of Concomitant Medications (Safety Population)
16.2.4.4.3	Listing of Use of Rescue Medication (Safety Population)
16.2.4.5	Listing of Non-drug Treatment/Procedure (Intent-to-Treat Population)
16.2.4.6	Listing of Medications and Non-drug Treatments/Procedures received on Day 6 (Safety Population)

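### The secondary and exploratory efficacy tests exclude everyone who used rescue after randomization, although the protocol specifies ITT

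*SAP*

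**What the plan says.** SAP 4.1.3 defines the FAS as randomized subjects with a baseline NRS evaluation and a baseline score above 0 "that were not using any rescue medication (as defined in Section 5.1.7.4.2) starting from randomization to Day 5 Visit 2". It also removes subjects whose rescue began before the study and was still ongoing at randomization. On use, it says: "This population will be used for key secondary, other secondary and exploratory analyses". Three later sections repeat this:

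- SAP 5.1.7.2: "Key Secondary analyses will be based on the FAS population".
- SAP 5.1.7.3: "Other Secondary Analyses will be based on the FAS population".
- SAP 5.1.7.4.1, average, worst and least pain: summarized "with descriptive statistics for FAS population by treatment group and by analysis timepoint", followed by ANCOVA.

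Rescue is defined broadly in SAP 5.1.7.4.2. It covers permitted paracetamol, other analgesic or anti-inflammatory drugs, and any non-drug therapy for pain. Protocol 6.4.4.3 allows paracetamol in both arms.

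Protocol 8.3.1.2 says of the secondary analyses: "These analyses will be based on the ITT population, using the ITT paradigm (i.e. as randomized"). The protocol synopsis puts efficacy in general under the ITT paradigm, and protocol 8.2 defines ITT as every randomized subject regardless of compliance.

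**The concern.** Rescue use is a consequence of pain after randomization. It is a component of the primary endpoint and an exploratory endpoint in its own right. Restricting SPID, RMDQ, mobility, time to acceptable pain (TTAP), time to no pain (TTNP), TOTPAR and the worst, least and average pain scores to subjects who never used it removes the worse-off subjects from each arm. The trial is open label with an untreated control, so there is no reason to expect removal at the same rate in both arms. The compared groups are then no longer those formed by randomization.

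The rule also conditions on the future. A subject who reports acceptable pain on Day 2 and takes paracetamol on Day 4 disappears from the TTAP analysis, event included. And the SAP treats one event in two ways: in the primary analysis a rescue user stays in the denominator as a non-responder, while in the secondary analyses the same subject is deleted.

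At stake are the key secondary p-values, which SAP 5.1.7.2.5 reads as confirmatory if the primary endpoint is significant. They would not estimate the effect of being assigned the patch.

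**Working it through.** **1. The texts side by side.** The protocol specifies ITT as randomized; the SAP specifies a rescue-free subset. SAP 5.1.11 lists population changes for patch-use and e-diary compliance but not this one. The revision history records that the FAS was added in version 3.0 and modified in version 4.0, with no reason given. The only sensitivity analysis (SAP 4.1.4 and 5.1.7.1) concerns the primary endpoint. In Appendix 1 the TTAP and TTNP tables are on the FAS, while the matching figures are labelled ITT, for example "Cumulative Incidence Curve for Time (hours) to Reach Acceptable Pain (Intent-to-Treat Population"). Curve and log-rank test would come from different subjects.

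**2. The plan's own sample size.** For 20% against 39% (mean 0.295), two-sided 5%, 80% power, pooled variance:

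n = [1.96 × √(2 × 0.295 × 0.705) + 0.8416 × √(0.20 × 0.80 + 0.39 × 0.61)]² / 0.19² = (1.264 + 0.531)² / 0.0361 = 89.3, so 90 per arm.

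180 / (1 − 0.10) = 200 randomized. Both stated figures reproduce. They concern the primary endpoint; the secondary endpoints have no power calculation.

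**3. Model for the FAS (assumed).** The documents give no rescue rate, no pain-rescue correlation and no effect size for the continuous endpoints. Let Y be a standardized outcome (higher is worse) with mean 0 in control, mean μ in the patch arm and SD 1. A subject uses rescue if L = rY + √(1 − r²)e exceeds a cut c, set to give the assumed control rescue rate. With a = c − rμ and λ = φ(a)/Φ(a):

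- fraction kept = Φ(a)
- mean of those kept = μ − rλ
- variance of those kept = 1 − r²(aλ + λ²)

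**4. True effect 0.43 SD, 90 per arm.** On all subjects, 0.43/√(2/90) = 2.885, which gives power 82%.

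Worked case, r = 0.7, control rescue 30% (c = 0.524):

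- Control: 70% kept (63 subjects), λ = 0.497, mean −0.348, variance 0.752.
- Patch: a = 0.825, 79.5% kept (71.6 subjects), λ = 0.357, mean −0.680, variance 0.793.
- Difference 0.332 SD, a shrinkage of 1 − 0.332/0.43 = 23%.
- SE = √(0.752/63 + 0.793/71.6) = 0.152; z = 2.19; power 59%.

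Part of this loss is numbers alone: an unbiased 0.43 SD with unit variance and 63 and 71.6 subjects gives 0.43/√(1/63 + 1/71.6) = 2.49, or 70% power.

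| r | Control rescue | Patch rescue (implied) | Shrinkage | Power |
|---|---|---|---|---|
| 0.3 | 10% | 8% | 2% | 78% |
| 0.3 | 30% | 26% | 4% | 67% |
| 0.5 | 20% | 15% | 10% | 70% |
| 0.5 | 30% | 23% | 12% | 64% |
| 0.5 | 40% | 32% | 14% | 57% |
| 0.7 | 10% | 6% | 12% | 74% |
| 0.7 | 20% | 13% | 18% | 66% |
| 0.7 | 30% | 20% | 23% | 59% |
| 0.7 | 40% | 29% | 26% | 51% |

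**5. No effect on pain, 100 per arm, rescue differing by arm for other reasons.** At r = 0.7 with rescue 30% control and 20% patch, the kept means are −0.348 and −0.245. The control arm looks better by 0.103 SD with SE 0.144, and the two-sided rejection rate is 11%. The full set:

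| Rescue, control / patch | r = 0.5 | r = 0.7 |
|---|---|---|
| 30% / 20% | 7.6% | 11% |
| 40% / 20% | 15% | 28% |
| 30% / 30% | 5% | 5% |

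The excess rejections favour the arm with more rescue. Swapping the rates between the arms gives the same totals in the patch's favour.

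**The case against.** Four points can be made for the plan.

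- **Not everything is on the FAS.** SAP 5.1.7.1 summarizes instantaneous pain on ITT as well as FAS, Tables 14.2.1.1 and 14.2.1.2 give pain perception and pain relief on ITT, and for rescue use, "Summary of Use of Rescue Medication will be based on the Safety population". This stands, and it limits the point to the inferential comparisons. None of that output is an ITT test.
- **The likely bias runs against the patch.** If untreated subjects take more tablets, the trimmed control arm looks better, and a false claim for the patch becomes less likely, not more. This stands for that direction only. More rescue in the patch arm would reverse it, and equal rates with equal selection cause no bias, only lost power.
- **The size is assumed.** Shrinkage runs from 2% to 26% over the grid above, and 0.43 SD is borrowed from the Cohen's h used for a binary endpoint. This stands: the figures illustrate what can happen and do not predict it. The departure from the protocol and the selection on outcome do not depend on them.
- **Rescue masks the patch effect, so its users should go.** This fails. Deleting users does not estimate the effect that would be seen without rescue; it compares two differently selected groups.

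The primary endpoint is indeed untouched, because rescue users remain in the mITT population as non-responders. For the exploratory endpoints, the ITT requirement rests on the general statement in the protocol synopsis, not on 8.3.1.2.

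**Conclusion.** The concern holds. Every planned between-group test of a secondary or exploratory efficacy endpoint is made on a subset defined by an outcome-related event after randomization. This contradicts protocol 8.3.1.2 and is not declared in SAP 5.1.11. No ITT test of these endpoints is planned, although the key secondary ones can become confirmatory.

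The size cannot be fixed from the documents. At the higher correlation considered, an effect of 0.43 SD would lose about a fifth to a quarter of its size and power would fall to between 66% and 51%; at low correlation most of the harm is lost numbers. The direction depends on which arm uses more rescue, and that will not be known until the data are seen. It should be corrected before the analysis is run.

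**What to change.** Remove the rescue-use exclusion from SAP 4.1.3. Run the key secondary, other secondary and exploratory efficacy analyses on all randomized subjects with a baseline NRS above 0, as randomized, using diary scores whether or not rescue was taken. Keep the rescue-free set only as a supplementary analysis, labelled as such. Put the TTAP and TTNP tables, tests and figures on one set. List in SAP 5.1.11 any remaining departure from the protocol's ITT, including the exclusion of subjects with baseline NRS 0.

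State the strategy for rescue explicitly. Using scores regardless of rescue means the estimate includes the effect of permitted paracetamol. If the team wants the secondary endpoints to match the primary, a composite version in which rescue counts as an unfavourable outcome can be added on the same randomized set.

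The cost is SAP wording and a re-run of planned programs; the diary data are already scheduled for every subject.
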